9.2.5 Week 5 (Final Visit: End of Treatment or Early Discontinuation)

At the Week 5 visit (final visit: end of treatment or early discontinuation), the following assessments will be performed by the Investigator or designee:

- Ask the patient to complete the Wound-QoL questionnaire before any other visit assessment.

- Review the diary and examine used bottles and any unused bottles of study treatment.
- Record concomitant medications.
- Measure vital signs (blood pressure, pulse, temperature).
- Collect blood for measuring HbA1c and for standard hematology and serum chemistry parameters.
- Perform a brief physical examination.
- Assess the wound(s) appearance, granulation tissue, exudate, drainage, surrounding erythema and/or swelling, and any signs of infection.
- Measure the wound(s) size pre-treatment (pre-debridement) with a standard, single-use, disposable ruler using the clock method (see Section 10.3 and Section 15, Appendix 2).
- Photograph the wound(s) pre-treatment (pre-debridement) using the study camera and a standard, single-use, disposable ruler to indicate relative size.
- Clean the wound(s) and wound area(s) with Prontosan solution per the institutional guidelines and Prontosan IFU for the individual patient wound(s).
- Assess the patient for any AEs.
- Measure the wound(s) size post-cleaning (post-debridement) with a standard, single-use, disposable ruler using the clock method.
- Photograph the wound(s) post-cleaning (post-debridement) using the study camera and a standard, single-use, disposable ruler to indicate relative size.
- Apply Prontosan gel to the wound(s) and apply the bandage/dressing per the institutional guidelines and the Prontosan IFU for the individual patient wound(s).

Patients who prematurely withdraw from the study for any reason should complete these early discontinuation visit requirements. If the early discontinuation visit is not done, the reason(s) will be recorded in the eCRF. Patients who withdraw or are withdrawn before completion of the Week 2 assessments and the Week 3 Wound-QoL questionnaire will be replaced to ensure that at least 52 patients will complete the study.

9.2.6 Unscheduled Visits

The Investigator may at his/her discretion arrange for a patient to have an unscheduled assessment, especially in the case of AEs or ADEs that require follow-up. The unscheduled visit page in the eCRF must be completed.

10 CLINICAL OUTCOME ASSESSMENTS

In this study, clinical outcome will be assessed by evaluating patient-reported QoL and Investigator-reported wound(s) size and assessments.

10.1 Wound Quality of Life Questionnaire

The Wound-QoL questionnaire measures the health-related QoL of patients with chronic wounds (see Section 15, Appendix 1). This short, validated questionnaire was developed based on the Freiburg Life Quality Assessment for wounds, the Cardiff Wound Impact Schedule, and the Wurzburg Wound Score.^{13,15} The questionnaire is self-explanatory, and

patients fill it in themselves. The Investigator or designee should instruct patients to check off only 1 box per line, in a box (not between boxes), and to answer all questions. In this study, patients are to complete the questionnaire during each week (Weeks 0-5). This questionnaire should be the first task performed at each visit. After the patient completes the questionnaire, the Investigator or designee should check that the questionnaire was completed legibly and completely.

The questionnaire consists of 17 statements of impairments. The patient assesses and documents the degree to which the impairments affected him/her within the previous 7 days by ticking checkboxes using a Likert scale from 0 to 4: 0=not at all, 1=a little, 2=moderately, 3=quite a lot, 4=very much. The global score, an average of all 17 items, reflects 3 QoL dimensions—Body (5 items), Psyche (5 items), and Everyday Life (6 items)—plus 1 item about financial burden. Subscores on the Body, Psyche, and Everyday Life QoL dimensions are calculated by averaging the respective items in these subscales: the Body subscale consists of Items 1-5, the Psyche subscale consists of Items 6-10, and the Everyday Life subscale consists of Items 11-16. Item 17, the statement about financial burden, does not belong in any of the subscales.^{14,15,16}

If more than 1 box is checked within an item, or if a patient has checked between 2 checkboxes, the item is treated as missing. Missing items are not averaged in the global score. A global score can be computed only if at least 75% of the items have been answered and are not treated as discarded or as missing (at least 13 of the 17 items are valid), and a subscore can be computed only if no more than 1 item of the subscale is missing.^{14,15,16}

10.2 Wound Assessment

The subject may have 2 chronic wounds below 1 knee or 1 chronic wound below each knee or only 1 chronic wound below either knee.

At screening, the Investigator or designee will collect the wound history for the wound(s), including wound type, wound age, location, past complications, and current dressing change frequency.

At each visit, the Investigator or designee will assess the wound(s) in terms of the wound appearance, granulation tissue, exudate, drainage, surrounding erythema and/or swelling, and any signs of infection.

10.3 Wound Measurement and Photography

The size of the wound(s) will be measured at screening (Week 0), and pre-treatment (pre-debridement) and post-cleaning (post-debridement) at each subsequent visit (Weeks 1, 2, and 5), and the wound(s) will be photographed pre-treatment and post-cleaning at Weeks 1, 2, and 5. For consistency, whenever possible, the same evaluator at each site should perform the measurements and photography across visits.

Wounds are to be measured using the clock method with the standard, single-use, disposable rulers. With this technique, you will generate an imaginary box around the wound by measuring the longest length and the greatest width using the body orientation as an imaginary clock (12:00 is the head, and 6:00 is the feet).

Document all measurements in centimeters (cm) and calculate the surface area of the wound (length x width) in cm². Further details for using the clock method are presented in Section 15, Appendix 2.

Photographs are to be taken only with the digital camera provided to the site by the Sponsor. Specific camera instructions, along with general guidelines for preparing the patient and the room and for taking wound photographs, are described in the photography manual to be provided to the site.

11 SAFETY ASSESSMENTS

Safety assessments, including vital signs, physical examinations, AE and ADE review, and clinical laboratory tests, are to be performed at the visits specified in the schedule of assessments in Table 1.

11.1 Vital Signs

Vital signs (systolic and diastolic blood pressure measurements, pulse rate, and temperature) will be evaluated at screening and at the Week 5 (end of treatment or early discontinuation) visit. All vital signs will be measured after the patient has been resting in a sitting position for at least 5 minutes. Body weight and height will also be recorded (screening visit only).

Out-of-range blood pressure or pulse rate measurements will be repeated at the Investigator's discretion. Vital sign measurements will be repeated up to 2 times, with a rest of at least 5 minutes between readings. All clinically significant changes from baseline must be recorded as AEs.

11.2 Physical Examination

A complete physical examination (head, ears, eyes, nose, throat, heart, lungs, abdomen, skin, cervical and axillary lymph nodes, neurological, and musculoskeletal systems) will be performed at the screening visit. A brief physical examination will be performed at the Week 5 visit (end of treatment or early discontinuation). Physical examinations will be performed by the Investigator or other designated study physician. Medical history will be recorded at screening, and concomitant illnesses will be recorded up to the first treatment at Week 1. Wound history, recorded at screening and Week 1, will include wound type(s), wound age(s), location, past complications, and current dressing change frequency.

All clinically significant changes from baseline must be recorded as AEs.

11.3 Laboratory Assessments

Blood samples are to be obtained at screening for glycated hemoglobin and standard clinical laboratory assessments (Table 2) if results are not available for tests performed within 1 month prior to screening. At the Week 5 visit (end of treatment or early discontinuation), blood samples will be obtained for clinical laboratory assessments. The amount of blood obtained from each patient in this study should not exceed 30 mL. Blood samples will be analyzed at the local (site) laboratory.

Table 2 Clinical Laboratory Assessments

Hematology	Serum Chemistry
Full and differential blood count	Albumin
Hematocrit (Hct)	Alanine aminotransferase (ALT)
Hemoglobin (Hb)	Alkaline phosphatase (ALP)
Mean corpuscular hemoglobin (MCH)	Aspartate aminotransferase (AST)
Mean corpuscular hemoglobin concentration (MCHC)	Blood urea nitrogen (BUN) or urea
Mean corpuscular volume (MCV)	Carbon dioxide (CO ₂)
Platelet count	Creatinine
Red blood cell (RBC) count	Creatine kinase and subtypes
White blood cell (WBC) count with differential	Electrolytes (Na, K, Cl, Ca, P)
	Gamma-glutamyl transpeptidase (GGT)
	Glucose
	Lactate dehydrogenase (LDH)
	Total bilirubin
Glycated hemoglobin (HbA1c)	Direct bilirubin

11.4 Adverse Events

11.4.1 Adverse Events

An AE is any symptom, physical sign, syndrome, or disease that either emerges during the study or, if present at screening, worsens during the study, regardless of the suspected cause of the event. All medical and psychiatric conditions (except those related to the indication under study) present at screening will be documented in the medical history eCRF. Changes in these conditions and new symptoms, physical signs, syndromes, or diseases should be noted on the AE eCRF during the rest of the study. Clinically significant laboratory abnormalities should also be recorded as AEs.

Adverse device effects (ADEs) are defined as AEs that are considered related to the study device. Possible anticipated ADEs with Prontosan solution or Prontosan gel include burning sensation, itching, and rash. In rare cases (1:10,000), anaphylactic shock has been reported after use of Prontosan solution or Prontosan gel.^{9,10}

Patients and/or caregivers will be instructed to report AEs in the diary, and patients will be monitored for AEs at each study visit. All AEs are to be followed until resolution or until a stable clinical endpoint is reached.

Each AE is to be documented in the eCRF with reference to start and stop dates, frequency, severity, relationship to study device (related: yes or no), action taken with study device, treatment of event, and outcome. Furthermore, each AE and each ADE are to be classified as being serious or non-serious. Changes in AEs and AE resolution dates are to be documented in the eCRF.

For the purposes of this study, the period of observation for collection of AEs extends from the time the patient gives informed consent until the final visit. Follow-up of an AE, even

after the end of treatment, is required until the event resolves or stabilizes at a level acceptable to the Investigator.

Specific guidelines for classifying AEs by intensity are given in Table 3.

Table 3 Classification of Adverse Events by Intensity

Mild: An event that is easily tolerated by the patient, causing minimal discomfort and not interfering with everyday activities.
Moderate: An event that is sufficiently discomforting to interfere with normal everyday activities.
Severe: An event that prevents normal everyday activities.

When changes in the intensity of an AE occur more frequently than once a day, the maximum intensity for the event should be noted. If the intensity category changes over a number of days, then those changes should be recorded separately (with distinct onset dates).

11.4.2 Serious Adverse Events and Serious Adverse Device Effects

An AE is considered “serious” if in the view of either the Investigator or Sponsor, it meets 1 or more of the following criteria:

- Is fatal
- Is life-threatening
- Results in inpatient hospitalization or prolongation of existing hospitalization
- Results in a persistent or significant incapacity or substantial disruption of the ability to conduct normal life functions
- Is a congenital anomaly/birth defect

Other important medical events that may not be immediately life-threatening or result in death or hospitalization, based upon appropriate medical judgment, are considered serious AEs (SAEs) if they are thought to jeopardize the patient and/or require medical or surgical intervention to prevent one of the outcomes defining an SAE.

A serious ADE is an ADE that has resulted in any of the consequences characteristic of an SAE.

11.4.3 Serious Adverse Event Reporting

An SAE occurring during the study must be reported to the Sponsor or designee (details for reporting will be in the Safety Plan and on the SAE form). Any such SAE due to any cause, whether or not related to the study device, must be reported within 24 hours of occurrence or when the Investigator becomes aware of the event. Notification can be made with the SAE reporting form as described in the following paragraphs:

1. Contact the study safety team to inform them that you are faxing an SAE form. The study safety team is available 24 hours a day, 7 days a week. If you are unable to speak with a live safety associate, leave a message with the name of the Investigator, your name, the telephone number where you can be reached, and the protocol number and title.
2. Fax the SAE form and any supporting documentation to the study safety team within 24 hours of becoming aware of the event. Verify successful transmission by

obtaining a Fax Confirmation Report; this confirmation page should be kept with the SAE report in case future monitoring is required.

The event must also be recorded on the AE eCRF. Preliminary reports of SAEs must be followed by detailed descriptions later on, including clear and anonymized photocopies of hospital case reports, consultant reports, autopsy reports, and other documents when requested and applicable. SAE reports must be made whether or not the Investigator considers the event to be related to the study device.

Appropriate remedial measures should be taken to treat the SAE, and the response should be recorded. Clinical, laboratory, and diagnostic measures should be employed as needed in order to determine the etiology of the problem. The Investigator must report all additional follow-up evaluations to the Sponsor Study Physician within 10 calendar days. All SAEs will be followed until the Investigator and Sponsor agree the event is satisfactorily resolved. The Sponsor will report SAEs to the FDA.

Suspected unexpected serious adverse reactions (SUSARs) are serious ADEs that have not previously been documented in the protocol or other safety information. SAEs which are attributed by the Investigator to the patient's underlying medical condition and unrelated to the study device will not be reported as SUSARs. The Sponsor is responsible for expedited reporting of SUSARs to the FDA; expedited reporting requires a preliminary report within 7 days for fatal or life-threatening cases, with another 8 days for completion of the report, and within 15 days for all other SUSARs.

The Investigator is responsible for notifying the Institutional Review Board (IRB).

12 STATISTICAL ANALYSIS

A Statistical Analysis Plan (SAP) will be prepared after the protocol and eCRF are approved. This document will provide further details regarding the definition of analysis variables and analysis methodology to address all study objectives. The SAP will serve as a complement to the protocol and supersedes it in the case of any differences.

The statistical evaluation will be performed using the Statistical Analysis Software (SAS®) Version 9.2 or higher (SAS Institute, Cary, NC). All data will be summarized using descriptive statistics, and where necessary, data will also be listed. For continuous variables, data will be summarized with the number of patients (N), mean, standard deviation (SD), median, minimum, and maximum. For categorical variables, data will be tabulated with the number and proportion of patients for each category.

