8.2 Dosage Schedule

The frequency and method of application will be per the institutional guidelines and the Prontosan IFU for the individual patient wound(s). Prontosan solution and Prontosan gel are to be used according to these guidelines during the 4-week treatment period. Prontosan solution will be used to rinse and clean the wound(s) and the surrounding area; bandages or dressings may be soaked in the solution and/or the gel and used for cleaning as required. After the wound(s) has/have been cleaned (and in the clinic, measured and photographed), Prontosan gel will be applied directly as a 3-5 mm coating on shallow flat wound surfaces or deep wound fissures. Bandages or dressings will then be applied per institutional guidelines and Prontosan IFU.^{9,10}

When patients are at a clinic visit, the Investigator or designee will administer study treatment. At Weeks 1 and 2, the Investigator or designee will dispense enough Prontosan solution and Prontosan gel for the patient's treatment until the next study visit. The patient (and/or the patient's caregiver) will be trained to administer the treatment at home, and the patient will be given a diary and trained to record the date and time of each treatment and any reactions to treatment. Patients (and/or caregivers) will also be instructed to record the liquid level remaining after each use, and to return all used bottles and any unused bottles of study treatment at the next visit for product accountability.

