13.2.2 Institutional Review Board

Conduct of the study must be approved by an appropriately constituted IRB. Approval is required for the study protocol, any protocol amendments, and ICFs.

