13.8 Protocol Amendment and Protocol Deviation

13.8.1 Protocol Amendment

Amendments to the protocol that entail corrections of typographical errors, clarifications of confusing wording, changes in study personnel, and minor modifications that have no impact on the safety of patients or the conduct of the study will be classed as administrative amendments and will be submitted to the IRBs for information only. The Sponsor or its designee will ensure that acknowledgement is received and filed. Amendments that are classed as substantial amendments must be submitted to the IRBs for approval.

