Appendix 2: Wound Measurement with the Clock Method

Wounds are to be measured using the clock method with the standard, single-use, disposable rulers. With this technique, you will draw an imaginary box around the wound at the longest length and the greatest width of the wound, using the body orientation as an imaginary clock (12:00 is at the head, 6:00 is at the feet). Do not slant the ruler to accommodate the greatest measurement, and remember that sometimes length is smaller than width. You will measure the length and width, in centimeters (cm), of the imaginary box. To measure a wound on the feet, use the heels as 12:00 and toes as 6:00.¹⁷

To measure the greatest length of the wound (regardless of shape), use the following steps:

1. Picture the face of the clock lying over the wound bed with 12:00 pointing toward the patient's head and 6:00 toward the patient's feet.
2. Locate the part of the wound that is closest to 12:00 and draw a line (in your mind) from that point straight across the body.
3. Locate the part of the wound that is closest to 6:00 and draw another line (in your mind) from that point straight across the body.
 - Now you have 2 parallel lines framing the top and bottom of the wound.
4. Place a standard, single-use, disposable ruler between these 2 parallel lines to measure the greatest length in cm.

To measure the greatest width of the wound, use the following steps:

5. Locate the part of the wound that is closest to 9:00 and draw a line (in your mind) at that point straight up and down (head to foot).
6. Locate the part of the wound that is closest to 3:00 and draw another line (in your mind) at that point straight up and down.
 - Now you have 2 parallel lines framing the left and right sides of the wound, thus completing the imaginary box around the wound.
7. Place a standard, single-use, disposable ruler between these 2 parallel lines to measure the greatest width in cm.
8. Remember to document all measurements in cm.

At this point, you have the maximum length (instructions 1 to 4) and the maximum width (instructions 5 to 7) of the wound. You can now calculate the surface area of the wound (length x width) in cm². To qualify for this study, the wound must be between 5 cm² and 50 cm², inclusive.

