3. STUDY DESIGN

This is a prospective, open-label, multi-site, single-arm study in patients with chronic leg wound(s). The investigator or designee will apply Prontosan solution and Prontosan gel to the wound(s) at clinical visits Week 1, Week 2, Week 5. Patients will apply Prontosan solution and Prontosan gel themselves (or have them applied by a caregiver) at home (Week 3 and Week 4). The study contains Screening period (Week 0), 4 weeks of treatment period (Week 1 – Week 5), and safety follow-up.

The schedule of assessments to be performed throughout the study is given in the protocol.

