Appendix 2: Wound Measurement with the Clock Method

Wounds are to be measured using the clock method with the standard, single-use, disposable rulers provided by the Sponsor. With this technique, you will draw an imaginary box around the wound at the longest length and the greatest width of the wound, using the body orientation as an imaginary clock (12:00 is at the head, 6:00 is at the feet). Do not slant the ruler to accommodate the greatest measurement, and remember that sometimes length is smaller than width. You will measure the length and width, in centimeters (cm), of the imaginary box. To measure a wound on the feet, use the heels as 12:00 and toes as 6:00.¹⁰

To measure the greatest length of the wound (regardless of shape), use the following steps:

1. Picture the face of the clock lying over the wound bed with 12:00 pointing toward the patient's head and 6:00 toward the patient's feet.
2. Locate the part of the wound that is closest to 12:00 and draw a line (in your mind) from that point straight across the body.
3. Locate the part of the wound that is closest to 6:00 and draw another line (in your mind) from that point straight across the body.
 - Now you have 2 parallel lines framing the top and bottom of the wound.
4. Place a standard, single-use, disposable ruler between these 2 parallel lines to measure the greatest length in cm.

To measure the greatest width of the wound, use the following steps:

5. Locate the part of the wound that is closest to 9:00 and draw a line (in your mind) at that point straight up and down (head to foot).
6. Locate the part of the wound that is closest to 3:00 and draw another line (in your mind) at that point straight up and down.
 - Now you have 2 parallel lines framing the left and right sides of the wound, thus completing the imaginary box around the wound.
7. Place a standard, single-use, disposable ruler between these 2 parallel lines to measure the greatest width in cm.
8. Remember to document all measurements in cm.

At this point, you have the maximum length (instructions 1 to 4) and the maximum width (instructions 5 to 7) of the wound. You can now calculate the surface area of the wound (length x width) in cm^2 . To qualify for this study, the wound must be between 10 cm^2 and 16 cm^2 , inclusive.

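### The clause that lets the SAP supersede the protocol is not limited to statistical methods, and the SAP restates eligibility, visit-window and adverse-event rules that differ from the current protocol

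*Protocol*

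**What the plan says.** The introduction to Protocol Section 12 first describes the SAP's task: "This document will provide further details regarding the definition of analysis variables and analysis methodology to address all study objectives". It then sets the order of precedence: "The SAP will serve as a complement to the protocol and supersedes it in the case of any differences".

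Changes of conduct have their own route. Protocol 13.2.2 states: "Approval is required for the study protocol, any protocol amendments, and ICFs". The SAP is not in that list. Protocol 13.8.1 adds: "Amendments that are classed as substantial amendments must be submitted to the IRBs for approval".

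The two documents differ on conduct in these places:

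- **Wound area.** Protocol Appendix 2 says a qualifying wound "must be between 5 cm² and 50 cm², inclusive", in line with inclusion criterion 3 in Section 7.1. SAP Appendix 2 says it "must be between 10 cm^2 and 16 cm^2".
- **Screening to baseline.** Protocol 6.1, 9.2.1, 9.2.2 and Table 1 give 1 week ± 1 day. SAP 5.1.4 gives at most 1 week, with a 1-day window either side.
- **Adverse-event intensity.** Protocol 11.4.1 asks for separate records, each with its own onset date, when the intensity category changes over several days. SAP 5.2.6 has one maximum intensity captured for the whole event.

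SAP Appendix 2 also specifies rulers supplied by the Sponsor, which Protocol Appendix 2 does not. No analysis depends on that.

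**The concern.** A precedence clause is useful when the SAP refines a model or a derivation. It becomes a problem when it is unrestricted and the SAP also restates design text. Each mismatch then raises the question of which document governs, and the literal answer is the SAP, although the IRB route in Protocol 13.2.2 and 13.8.1 runs through the protocol.

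The SAP uses these rules to produce results. SAP 5.1.6 summarises violations of the entry criteria and Listing 3 lists them. SAP 4.1 defines the Enrolled Population by those criteria, and SAP 5.1.5 makes it the denominator for disposition. SAP 5.1.4 removes out-of-window assessments from the descriptive analysis and from the primary and secondary endpoints. Two programmers could follow the documents in good faith and produce different deviation counts, different denominators and different sets of usable baselines.

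**Working it through.** **1. The plan's own figure.** Inputs from Protocol 12.1 and SAP 5.1.3: mean change 0.35, SD of differences 0.88, two-sided 0.05, paired t-test, 80% power. With noncentrality (0.35/0.88)·√n and n − 1 degrees of freedom, exact power is 79.5% at n = 51 and 80.3% at n = 52. So 52 is the smallest n that reaches 80%, and the figure reproduces. Both documents state the same calculation and the precedence clause does not enter it.

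**2. Wound area.**

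- Protocol range: 50 − 5 = 45 cm².
- SAP range: 16 − 10 = 6 cm², wholly inside the protocol range.
- Share of the range: 6/45 = 13.3%. The remaining 39 of 45 cm² (86.7%) is eligible under the protocol and not under the SAP appendix.

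These are shares of the range, not of patients. The documents give no distribution of wound areas, so the number of patients affected cannot be derived. As an illustration, a patient whose only wound measures 30 cm² is eligible under the protocol and an inclusion violator under SAP Appendix 2.

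**3. Enrolled Population.** Suppose that all treated patients meet the protocol criteria and that a fraction f of them has no wound within 10 to 16 cm². With the SAP range applied, the Enrolled Population is (1 − f) times the Safety Population. The Safety row in the disposition table is then 1/(1 − f) of the denominator, which is above 100% for any f > 0. If instead the table is restricted to enrolled patients, the fraction f of treated patients disappears from it.

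**4. Baseline window.** Count screening as day 0.

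- Protocol: 7 ± 1, that is days 6 to 8.
- SAP 5.1.4: no later than day 7, plus 1 day, with no stated lower limit.

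The upper limit is day 8 in both. A visit on day 3 is in window under the SAP wording and out under the protocol wording. If it is treated as out, SAP 5.1.4 removes the baseline score and the patient has no change score. That patient can still be in the Evaluable Population, which requires only 2 weeks of treatment and the Week 3 questionnaire, but contributes nothing to the paired test.

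**5. Adverse events.** An event that moves from mild to moderate over several days gives two records under Protocol 11.4.1 and one under SAP 5.2.6. The listing and the database differ. Summaries that count patients are largely protected, because they count each patient once and Protocol 12.6 takes the greatest severity.

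**The case against.** The strongest reply is that the clause was never meant to reach conduct. It stands under the heading for statistical analysis, directly after a sentence that confines the SAP to analysis variables and methodology, and it calls the SAP a complement. Conduct changes go through the IRB under 13.2.2 and 13.8.1. The SAP itself defers to the protocol: SAP 3 refers to the protocol for the schedule of assessments. SAP 5.1.4 points to a flowchart called Table 1, which appears to be the protocol's schedule because the SAP's own Table 1 is patient disposition. Correcting the individual SAP lines would remove the known conflicts whatever the clause says.

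Most of this stands. A reader might infer that outdated SAP text definitely outranks the IRB-approved protocol, and the documents do not support that: the literal wording points one way and the context the other. Nor do they show that the IRB did not see the SAP. Section 13.2.2 lists what requires approval, not what was submitted.

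A reader might also take SAP 3 to rule out home treatment before Week 3, because it mentions home application for Weeks 3 and 4. The passage does not say that these are the only weeks. It can be read as contrasting clinic visits with weeks that have no visit, and no planned analysis separates home from clinic exposure.

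The narrower reading does not settle the matter, though. Visit windows, deviation categories and population definitions lie between conduct and analysis. A reader who confines the clause to analysis could still apply the SAP's version to them. SAP 5.1.4 is itself unclear: it states one baseline rule and cites a schedule that appears to state another.

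**Conclusion.** The point holds as an ambiguity with specific consequences. The clause has no written limit, and at least three SAP statements on conduct (wound area, baseline window, adverse-event intensity) differ from the current protocol. Followed literally, the SAP would class patients who are eligible under the protocol as violators over 39 of the 45 cm² range, distort the disposition denominator, and apply a baseline window with no stated lower limit.

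The consequences are bounded. The primary test, its hypotheses and N = 52 are the same in both documents. The Evaluable Population is not defined by wound area, so that conflict does not alter the primary analysis set. The window conflict can alter which baselines are usable, but the documents do not allow an estimate of how many. Precedence of the SAP on statistical methods is legitimate and should stay.

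The conclusion rests on the current text of both documents and assumes that the SAP wording in 5.1.4, 5.2.6 and Appendix 2 would be applied as written.

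**What to change.** In Protocol Section 12, replace the precedence sentence with wording such as: *The SAP may refine or replace the statistical methods in Section 12. For eligibility, study procedures, visit windows and the collection and reporting of safety data, the protocol governs.*

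In the SAP, replace the restated eligibility, window and measurement text in 5.1.4 and Appendix 2 with a reference to the current protocol version. The sponsor should reconcile SAP 5.1.4, 5.2.6 and Appendix 2 with the corresponding protocol sections before deviations are classified and populations assigned, and should state which baseline window the out-of-window rule uses.

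The cost is one protocol sentence, handled through the amendment route, and a short SAP revision. It needs no new assessments and no change to the sample size or the primary test.
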